Sponsor (in Dutch: verrichter/opdrachtgever)	University Medical Center Groningen
Subsidising party	BeNeFit Call Funding Members (ZonMw/KCE)
Independent expert (s)	Dr. [name], neurologist, University Medical Center Groningen
Laboratory sites <if applicable>	NA
Pharmacy <if applicable>	NA

Version	Changes
2.2 21-04-2023	
Accepted by METC (Netherlands)
 
6.1: Removal of Carotid Artery Stent Cristallo Ideale, Medtronic → out of stock
 
6.5: moved to 7.5
 
6.6 moved to 7.6
 
8.2: removal of “and administration of prior IVT”
 
10.2: addition of “estimated with proportional odds regression
 
10.2: removal of “Predefined subgroup analyses will be performed to test for interaction between specific variable and the treatment.”
 
10.4: Addition of “For the subgroup analyses, the point estimates with confidence intervals per subgroup will be presented with the p value for interaction, obtained from the difference in model fit of a model with and without interaction term (treatment * concerning subgroup, where applicable as a continuous variable) tested with a likelihood ratio test. “

2.3 08-05-2023	
Accepted by CEC (Belgium)
 
17.7: Addition of “Uw gegevens worden gepseudonimiseerd. Dit betekent dat ze gecodeerd worden (uw identiteit zal vervangen worden voor een identificatiecode in de studie, die apart wordt bewaard.”
 
17.7: Removal of “De onderzoekers schrijven uw naam nergens op. En zij vertellen aan niemand dat u aan het onderzoek heeft meegewerkt.”
 
17.8: Addition of “Your data will be pseudonymised. This means they will be encrypted (your identity will be replaced by an identification code in the study, which will be stored separately).”
 
17.8: Removal of: “This means that they are not traceable to you. The researchers do not tell anyone that you participated in the study”
 
17.8: Addition of: “Vos données seront pseudonymisées. Cela signifie qu'elles seront cryptées (votre identité sera remplacée par un code d'identification dans l'étude, qui sera conservé séparément). »
 
17.8 Removal of : Autrement dit, celles-ci ne permettront pas de vous identifier. Les chercheurs ne dévoilent à personne que vous avez participé à l'étude. »

2.4 25-07-2023	
5.3: Addition of “or optifibatide IV (bolus of 180 microgram/kg followed by 2.0 microgram/kg/min)”
 
7.1: Addition of Aspiration catheter React by Medtronic.
 
8.1.3: Addition of “Subarachnoid hemorrhage within 90 days”
 
8.1.4: Study parameters: added such as but not limited to for all parameters and examples
 
8.3: Removal of “For all included patient, the stroke severity at baseline, at 24 hours and at day 5-7 (or at discharge) is evaluated with the NIHSS score.”
 
8.4: anonymised → anonymized
 
8.6: communicate to the patients or legal representatives who do not consent, that we will anonymously register at least SAE's
 
9.2.2: is a congenital anomaly or birth defect (not applicable for CASES)
 
12.1: Removal of “digitally”
 
12.1: Addition of “Pseudonymized imaging data should be sent as DICOM files to the imaging core lab.
 
17: Questionnaires: changed French Euro-Qol 5D-5L from Paper Interviewer Administration to Paper Self-Complete version so that it matches English and Dutch versions
 
17: Questionnaires: IMTA-MCQ and IMTA-PCQ added version numbers and changed so that the English, Dutch and French versions so that they match.

## LIST OF ABBREVIATIONS AND RELEVANT DEFINITIONS

A1	A1 segment of the anterior cerebral artery
ABR	General Assessment and Registration form (ABR form), the application form that is required for submission to the accredited Ethics Committee; in Dutch: Algemeen Beoordelings- en Registratieformulier (ABR-formulier)
ADL	Activities of Daily Living
AE	Adverse Event
AR	Adverse Reaction
ASPECTS	Alberta Stroke Program Early CT Score
BMT	Best Medical Treatment
CA	Competent Authority
CAS	Carotid Artery Stenting
CASES	Carotid Artery Stenting during Endovascular treatment for acute Stroke
CCMO	Central Committee on Research Involving Human Subjects; in Dutch: Centrale Commissie Mensgebonden Onderzoek
CEA	Carotid endarterectomy
CI	Confidence Interval
CONTRAST	COllaborations for New TReatments of Acute Stroke
CT	Computed Tomography
CTA	Computed Tomography Angiography
CV	Curriculum Vitae
DSA	Digital Subtraction Angiography
DSMB	Data Safety Monitoring Board
EQ5D	Euro-QoL 5 dimensions
EU	European Union
EVT	Endovascular Thrombectomy
EudraCT	European drug regulatory affairs Clinical Trials
GCP	Good Clinical Practice
GDPR	General Data Protection Regulation; in Dutch: Algemene Verordening Gegevensbescherming (AVG)
IB	Investigator's Brochure
IC	Informed Consent
ICA	Internal carotid artery
ICH	Intracerebral hemorrhage
IMP	Investigational Medicinal Product
IMPD	Investigational Medicinal Product Dossier
Kg	Kilogram
M1	M1 segment of the middle cerebral artery
M2	M2 segment of the middle cerebral artery

METC	Medical research ethics committee (MREC); in Dutch: medisch-ethische toetsingscommissie (METC)
Mg	Milligram
mRS	Modified Rankin Scale
NASCET	American Symptomatic Carotid Endarterectomy Trial
NIHSS	National Institute of Health Stroke Scale
cOR	common odds ratio
PI	Principal Investigator
PROBE	Prospective, Randomized, Open, Blinded End-Point
PTA	Percutaneous transluminal angioplasty
RCT	Randomized Clinical Trial
(S)AE	(Serious) Adverse Event
SPC	Summary of Product Characteristics; in Dutch: officiële productinformatie IB1-tekst
Sponsor	The sponsor is the party that commissions the organisation or performance of the research, for example a pharmaceutical company, academic hospital, scientific organisation or investigator. A party that provides funding for a study but does not commission it is not regarded as the sponsor, but referred to as a subsidising party.
SUSAR	Suspected Unexpected Serious Adverse Reaction
TIA	Transient Ischemic Attack
TICI	Thrombolysis In Cerebral Infarction
UAVG	Dutch Act on Implementation of the General Data Protection Regulation; in Dutch: Uitvoeringswet AVG
WMO	Medical Research Involving Human Subjects Act; in Dutch: Wet Medisch-wetenschappelijk Onderzoek met Mensen

## SUMMARY

**Rationale:** Approximately 20% of the patients with acute ischemic stroke due to an intracranial large vessel occlusion (LVO) has a high-grade stenosis in the ipsilateral cervical carotid artery. It is uncertain whether immediate carotid artery stenting (CAS) of a cervical carotid artery stenosis during endovascular thrombectomy (EVT) is beneficial. Immediate CAS could improve cerebral perfusion and prevent recurrent ischemic stroke but could also increase the chance of intracranial hemorrhagic complications due to hyperperfusion syndrome or to the required antiplatelet treatment to prevent stent occlusion. Moreover, some patients end up with a severe disabling stroke after EVT. In these patients carotid revascularization by carotid endarterectomy (CEA) or CAS would usually not be performed but these patients would be treated by medical management only.

**Objective:** to assess the safety and efficacy of immediate cervical CAS during EVT in patients with acute ischemic stroke due to LVO with a high-grade stenosis >50% or occlusion of the ipsilateral cervical carotid artery.

**Study design:** prospective randomized open label controlled trial comparing immediate CAS during EVT versus EVT with deferred treatment of the cervical carotid artery lesion (deferred CAS/CEA or medical management alone). Outcome assessment will be blinded for treatment allocation.

**Study population:** patients with acute ischemic stroke with a CT-angiography proven intracranial LVO in the anterior circulation (ICA, A1, M1 or M2) as well as an ipsilateral cervical carotid artery tandem lesion of presumed atherosclerotic origin with a stenosis >50% or an ipsilateral acute proximal internal carotid artery occlusion who are treated with EVT according to the guidelines.

**Intervention (if applicable):** in the intervention group, the cervical carotid artery lesion will be treated with a stent during the EVT (just before or directly after intracranial thrombus removal), the control group will be treated according to the national guidelines with carotid endarterectomy of carotid artery stenting (for patients with non-disabling stroke) or medical management alone (for patients with severe disabling stroke).

**Main study parameters/endpoints:** the primary endpoint is the modified Rankin Scale (mRS) score at 3 months after stroke onset. Ordinal logistic regression analyses will be done with adjustment for prognostic variables: age, sex, baseline NIHSS, prestroke mRS score, collateral score on baseline CTA and onset to reperfusion time.

**Nature and extent of the burden and risks associated with participation, benefit and group relatedness:** All patients are being treated with EVT according to the local guidelines. The patients allocated to the intervention group will undergo CAS during EVT, which carries a risk of cerebral hyperperfusion syndrome and subsequent intracerebral hemorrhage. The potential benefits of immediate CAS during thrombectomy include: an improvement of cerebral blood flow during and after EVT. A second benefit is a lower risk of recurrent stroke in the first 14 days compared to the deferred treatment strategy. A third benefit of immediate CAS is that the patient does not need a second invasive treatment (carotid revascularization surgery (CEA or CAS) during the rehabilitation period which again carries some risk of complications. At last, the immediate CAS approach is likely to reduce health care costs.

## 1. INTRODUCTION AND RATIONALE

Acute ischemic stroke is an important cause of death and disability. After introduction of IV thrombolysis, the management of acute ischemic stroke treatment has been further improved by mechanical thrombectomy for proximal intracranial occlusions.

Around 20% of the patients with proximal intracranial occlusion have a tandem lesion in the cervical ICA that may necessitate a different treatment approach during the EVT. Huge variation in clinical practice exists with regards to the management of these tandem lesions. While some interventionalists advocate immediate stenting of the cervical carotid artery lesion (CAS), others argue that the treatment of the tandem lesion should be deferred after the very acute phase of ischemic stroke.

The advantage of immediate CAS is improvement of cerebral blood flow, and prevention of early recurrent stroke or TIA. Some interventionalist do even feel that stenting is necessary to perform a successful intracranial thrombectomy. Further, in immediate CAS, patients do not have to undergo a second invasive treatment (CEA or CAS) for secondary prevention. However, a direct stenting approach may also carry some disadvantages. To prevent in-stent thrombosis dual platelet therapy is often prescribed for patients who are electively treated with CAS. However in the acute phase during EVT, administration of dual antiplatelet therapy could increase the risk intracerebral hemorrhage (ICH). Second, carotid revascularization could lead to a cerebral hyperperfusion syndrome especially in case of a chronic high grade proximal ICA stenosis. Cerebral hyperperfusion can lead to severe complications, such as ICH. In stent thrombosis may occur, especially in the hyperacute phase, if antiplatelet therapy is not administered and in stent thrombosis may lead to recurrent stroke.

A post-hoc analysis of the MR CLEAN trial has shown that the clinical outcome in the group of patients with cervical carotid artery stenosis was worse compared to patients without tandem lesions. In two large patient registries, it has been shown that among patients with tandem lesions treated with EVT, the immediate CAS group had better outcomes compared to the deferred treatment group. Others have found that immediate CAS was associated with an increased risk of intracranial hemorrhage, probably due to aggressive double antiplatelet therapy. Three systematic reviews and meta-analyses have been performed that included mostly retrospective and uncontrolled cohort studies. Two of these reports did not reveal major differences between an immediate CAS and a deferred strategy, while one meta-analysis suggested that the patients with immediate CAS had a greater likelihood of favorable outcome compared to deferred treatment strategy. Firm conclusions could not be drawn because of the study design and the high likelihood for both selection and publication bias of the included studies.

In carotid revascularization secondary prevention trials, CEA has shown to be slightly superior to CAS regarding the composite endpoint of recurrent stroke, myocardial infarction and/or death. Both CEA and CAS have been tested in patients with TIA or minor non-disabling stroke. It is uncertain which of the two strategies (acute stenting versus delayed CEA or CAS) is the most effective and safe approach during EVT in patients with acute stroke and a proximal ICA stenosis/occlusion.

This RCT will compare the efficacy and safety of two different strategies in patients undergoing EVT with an ipsilateral tandem lesion (proximal atherosclerotic ICA stenosis > 50% or occlusion and an ipsilateral proximal intracranial occlusion):

- immediate CAS during EVT (before or after the intracranial thrombectomy)
- EVT without immediate CAS during EVT (PTA of the proximal ICA stenosis/occlusion is allowed in order to perform the intracranial thrombectomy), but deferred treatment by carotid revascularization (CEA or CAS) according to the current guidelines (preferably within 2 weeks after stroke onset in patients who have recovered to a non-disabling stroke, or best medical management in case of a persistent disabling stroke).

## **2. OBJECTIVES**

The primary objective of this trial is to assess the efficacy of immediate CAS among patients with acute ischemic stroke treated with EVT and a severe ipsilateral proximal carotid artery stenosis (>50%) or occlusion and compare this with the strategy of deferred treatment (including best medical treatment without CEA/CAS) of the proximal carotid artery stenosis according to the guidelines.

The secondary objective is to compare the safety of the two strategies (immediate CAS versus deferred treatment) regarding the incidence of symptomatic intracerebral hemorrhage, recurrent stroke and early proximal carotid artery re-occlusion.

The tertiary objective is to compare the quality of life and cost-effectiveness of both strategies.

### **3. STUDY DESIGN**

This study is a phase 3 international multicenter randomized clinical trial with open label treatment and blinded outcome assessment (PROBE design). The study will be performed among thrombectomy capable stroke centers in the Netherlands and Belgium.

## 4. STUDY POPULATION

### 4.1 Population (base)

The study will be performed in patients with acute ischemic stroke due to proximal intracranial arterial occlusions and a severe ipsilateral proximal carotid artery stenosis (>50%) or occlusion, the so-called atherosclerotic tandem lesion. Approximately 2000 patients in the Netherlands and 1000 patients in Belgium are treated with EVT every year. Around 80% (n=2400) of these EVTs are performed in the anterior circulation (supplied by the carotid artery) and 20% in the posterior circulation (supplied by the vertebrobasilar arteries). This means that yearly around 360-480 (15-20% of 2400) patients with an ipsilateral cervical atherosclerotic carotid artery stenosis undergo EVT for acute ischemic stroke in the Netherlands and Belgium.

### 4.2 Participating centers

Each participating center should meet the following criteria in order to participate in the trial

- the center should be a stroke center with sufficient experience in EVT (>50 EVT's per year, >20 EVT's per interventionist per year)
- the center should have experience in conducting acute stroke trials
- the intervention team should have experience with CAS (at least 5 CAS procedures per interventionist performed)
- the EVT should be performed with devices approved by the steering committee
- the CAS should be performed with a CE marked stent approved to be used in the carotid artery and approved by the steering committee.
- all participating centers should offer deferred revascularization treatment (CEA or CAS) within 2 weeks after initial stroke onset.

### 4.3 Inclusion criteria

In order to be eligible to participate in this study, a subject must meet all of the following criteria:

- Acute ischemic stroke due to proximal intracranial occlusion in the anterior circulation (intracranial ICA, M1, proximal M2) on the CT angiography
- Stenosis >50% according to the NASCET criteria or initial occlusion of the ipsilateral cervical carotid artery of presumed atherosclerotic origin on baseline CT angiography
- Eligible for EVT according to the guidelines: EVT within 6 hours of onset or EVT between 6-24 hours after onset based on perfusion CT imaging selection (conform current guidelines)
- Baseline National Institute of Health Stroke Scale (NIHSS) score  $\geq 2$
- Age >18 years
- Written informed consent (deferred consent)

#### 4.4 Exclusion criteria

A potential subject who meets any of the following criteria will be excluded from participation in this study:

- Any intracranial hemorrhage
- Cervical carotid artery stenosis or occlusion with other causes than presumed atherosclerosis (e.g. carotid artery dissection, floating thrombus, carotid web)
- Any exclusion criterion for EVT according to the guidelines
- Pre stroke disability (defined as a modified Rankin Scale score >2)
- Recent gastro-intestinal or urinary tract hemorrhage (<6 weeks)
- Recent severe head trauma (<6 weeks)
- Recent infarction on baseline brain CT in the same vascular territory (< 6 weeks)
- Known allergy to aspirin and/or clopidogrel
- Pregnancy

#### 4.5 Sample size calculation

A non-inferiority design will be used. If immediate carotid artery stenting is not less effective compared to deferred treatment, immediate carotid artery stenting will be the new standard of care in this group of stroke patients. The justification for a non-inferiority design is as follows: when immediate CAS is not worse compared to the deferred treatment strategy, it will be implemented as standard practice because: 1) it will be highly cost-effective, as no second hospitalization is needed for a carotid revascularization procedure, and 2) the immediate CAS approach is a more patient friendly approach.

For the sample size calculation, we used data from the Dutch MR CLEAN registry, a nationwide cohort of EVT treated patients between 2014-2018. Based on the mRS distributions in the immediate CAS group (mRS 0: 17.9%, mRS 1: 22.3%, mRS 2: 16.7%, mRS 3: 14.4%, mRS 4: 12.3%, mRS 5: 5.0%, mRS 6: 11.4%) and in the deferred treatment group (mRS 0: 6.9%, mRS 1: 20.2%, mRS 2: 17.9%, mRS 3: 16.4%, mRS 4: 17.2%, mRS 5: 8.0%, mRS 6: 13.4%), we calculated the assumed effect size to be a common odds ratio (cOR) of 1.15 for a shift in favorable direction on the full mRS. The non-inferiority margin was set to a cOR of 0.8, corresponding to an absolute difference of approximately 5% in favorable outcome (mRS 0-2). This is a generally accepted margin in the stroke research community and has been recently used in comparable EVT trials. We used Monte Carlo simulations with 5000 runs to calculate the required sample size based on the assumptions above showing that a sample size of 610 patients, would provide 80% power (at a two-sided alpha level of 0.05) to determine that the lower bound of the cOR 95% confidence interval (CI) does not cross the non-inferiority margin of 0.8. Covariate adjustment for major prognostic variables that included age, pre-stroke mRS score, stroke severity, collateral score and time from symptom onset to randomization results in a reduction of at least 15% in the required sample size (n=520). Assuming a crossover rate of 3% in each arm (6% for both groups), necessitates an increase in sample size by factor  $1/(1 - \% \text{ crossover})^2 = 1/(1 - 0.06)^2 = 1.13$ . So taking crossovers into account, the sample size increases to 588 (520\*1.13). Based on the experience of the MR CLEAN NO-IV trial and MR CLEAN-MED trial, the number of patients lost to follow up is expected to be low

(0 in both recently completed trials). Assuming a combined percentage of 2% due to loss to follow up and to erroneous inclusions (for example inclusion of patients who appear to have carotid dissection or carotid pseudo-occlusion) the sample size will need to be increased to a total sample size of 600 patients (n= 300 per group).

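### The planning cOR of 1.15 does not follow from the registry distributions said to produce it (they give about 1.70), and at 1.15 the base size of 610 gives about 72% power, not 80%

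*Protocol*

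**What the plan says.** Protocol section 4.5 takes its planning data from a national registry of EVT-treated patients. For immediate CAS it gives "mRS 0: 17.9%, mRS 1: 22.3%, mRS 2: 16.7%, mRS 3: 14.4%, mRS 4: 12.3%, mRS 5: 5.0%, mRS 6: 11.4" (percent), and for deferred treatment "mRS 0: 6.9%, mRS 1: 20.2%, mRS 2: 17.9%, mRS 3: 16.4%, mRS 4: 17.2%, mRS 5: 8.0%, mRS 6: 13.4" (percent). Based on these distributions, it says, "we calculated the assumed effect size to be a common odds ratio (cOR) of 1.15 for a shift in favorable direction". It mentions no shrinkage, confounder adjustment or deliberate caution.

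The margin follows: "The non-inferiority margin was set to a cOR of 0.8, corresponding to an absolute difference of approximately 5% in favorable outcome (mRS 0-2"). Monte Carlo simulation with 5000 runs was used "to calculate the required sample size based on the assumptions above showing that a sample size of 610 patients" is needed. That number, the section says, "would provide 80% power (at a two-sided alpha level of 0.05"). The criterion for success is: "the lower bound of the cOR 95% confidence interval (CI) does not cross the non-inferiority margin of 0.8". After this, adjustment for covariates "results in a reduction of at least 15% in the required sample size (n=520"). A crossover factor of 1.13 raises this to 588, and 2% for loss to follow-up and erroneous inclusions raises it to 600.

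**The concern.** The cOR is the main driver of the sample size, and the whole chain 610, 520, 588, 600 rests on it. The text presents 1.15 as a calculated result and prints the inputs, so a reader can check it, and it fails by a margin that rounding or choice of method cannot explain. A reader then cannot tell which effect sized the trial.

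The second link matters more in practice. If 1.15 was the effect used, 610 should give the stated power at the stated alpha and margin. If it does not, the trial is planned with less power than an ethics committee, data monitoring board or funder has been told.

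**Working it through.** **Inputs (all Protocol section 4.5).** The two mRS distributions, cOR 1.15, margin 0.8, two-sided alpha 0.05, 80% power, base size 610, and steps of 15%, 6% and 2%.

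**1. Are the distributions usable?** Both sum to 100.0%, so a damaged digit is not evident.

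**2. Odds ratios at each cut-point**, immediate versus deferred, from the cumulative percentages:

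| mRS | Immediate | Deferred | Odds ratio |
|---|---|---|---|
| 0 | 17.9 | 6.9 | 2.94 |
| 0-1 | 40.2 | 27.1 | 1.81 |
| 0-2 | 56.9 | 45.0 | 1.61 |
| 0-3 | 71.3 | 61.4 | 1.56 |
| 0-4 | 83.6 | 78.6 | 1.39 |
| 0-5 | 88.6 | 86.6 | 1.20 |

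Example for mRS 0-2: (56.9/43.1)/(45.0/55.0) = 1.61. The lowest value is 1.20, so no weighted average of the cut-points can reach 1.15.

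**3. Common odds ratio.** The proportional-odds maximum likelihood fit gives 1.70 with equal groups, and 1.65 to 1.77 for group splits from 90:10 to 10:90. The geometric mean of the cut-points is 1.68. Other summaries also stay well above 1.15: win ratio 1.50, win odds 1.41.

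**4. Base sample size.** Whitehead's ordinal formula, with the effect measured from the margin:

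N = 12 (z_alpha + z_beta)² / {[ln(cOR) − ln(0.8)]² (1 − Σp̄³)}

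Here p̄ is the mean of the two arms' category probabilities. Applying cOR 1.15 to the deferred distribution gives 1 − Σp̄³ = 0.973 and ln(1.15/0.8) = 0.363. Then

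N = 12 × (1.960 + 0.842)² / (0.363² × 0.973), about 735 (735 to 737 whichever distribution is used as the base), against 610 stated.

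At cOR 1.70 the same formula gives about 171.

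**5. Power of 610 at cOR 1.15.** The standard error is √[12/(610 × 0.973)] = 0.142. Power = Φ(0.363/0.142 − 1.960), which is 72.3%. Simulation with a proportional-odds fit and 305 patients per arm gave 72.0%.

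**6. What would give 610?** At two-sided 0.05, a cOR of about 1.19 (1.18 needs 641, 1.20 needs 589). At one-sided 0.05 and cOR 1.15, N is about 580 and 610 patients give 81.8% power, but this is not the 95% interval criterion that the section states.

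**7. The remaining steps reproduce.** 610 × 0.85 = 518.5 (about 520); 520/0.94² = 588; 588/0.98 = 600. On the margin, odds of 45.0% multiplied by 0.8 correspond to 39.6%, a difference of 5.4 points, consistent with the stated 5%.

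**8. Carried to the final size.** Because steps 15%, 6% and 2% are applied as stated, the final 600 corresponds to the base of 610 and carries the same power, about 72%. Starting from 735: 735 × 0.85 = 625; 625/0.94² = 707; 707/0.98 = about 722.

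**The case against.** The best defence is that 1.15 is a confounder-adjusted or deliberately cautious figure. That is plausible. The base size of 610 lies close to what 1.15 to 1.19 would need and far from the 171 needed at 1.70, so something near 1.15 was probably used. A planning effect well below a raw registry contrast is also prudent. This stands as a likely explanation, but the section does not give it: it says the value was calculated and points to the unadjusted distributions. It also does not help with the second defect, because at 1.15 the size is too small for the stated power. Relabelling 1.15 as conservative would leave that untouched.

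A second defence is that covariate adjustment recovers power. It does, but the protocol has already spent that gain in reducing 610 to 520.

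A reader might infer from 1.70 that the trial would probably show superiority and ought to have planned a test for it, or that some 170 patients would be enough. The documents support neither. The 1.70 is an unadjusted, non-randomised contrast, and Protocol sections 1 and 6.3 themselves warn of selection and publication bias in the observational evidence. The non-inferiority design is chosen and justified in section 4.5. Such a trial need not test superiority, and a test could be set out in a statistical analysis plan that is not shown. Section 10.2 already has the cOR reported with its 95% confidence interval.

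**Conclusion.** The point holds as an internal contradiction with two parts. First, the printed distributions give an unadjusted cOR of about 1.70 with no cut-point below 1.20, so the statement that 1.15 was calculated from them is wrong as written. The document does not show whether the distributions or the described origin of 1.15 is at fault. Second, 610 follows from neither effect: at the stated 1.15 about 735 are needed and 610 give about 72% power instead of 80%, while at 1.70 about 171 would do.

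The power figures assume proportional odds, equal allocation, the stated margin, two-sided alpha 0.05, and the protocol's own 15%, 6% and 2% steps taken at face value. Formula and simulation agree to within half a percentage point. The result concerns a single analysis; any effect of requiring both the per-protocol and intention-to-treat analyses to succeed (Protocol section 10) is not included.

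**What to change.** In section 4.5:

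- State that the printed distributions give a cOR of about 1.70 (unadjusted registry data), and state where 1.15 comes from: a cautious choice with its reason, or an adjusted analysis with its method. If the distributions are misprinted, correct them instead.
- Restate the power so that effect, alpha, margin and sample size agree. With cOR 1.15, margin 0.8, two-sided 0.05 and the planned 600, that is about 72%. If the simulation used another effect or a one-sided alpha, say so and reconcile it with the 95% confidence interval criterion.

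This costs corrected wording and a re-run of the existing simulation. It changes no patient number, margin, alpha or analysis. If the sponsor wishes to keep 80% power at 1.15, the same chain leads to about 722 patients, 122 more than planned. That is a separate decision, and the correction does not depend on it.

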## **10. STATISTICAL ANALYSIS**

The statistical analysis and reporting of the trial will be in accordance with the CONSORT guidelines. Baseline data will be reported by treatment allocation as categorical or continuous variables, where appropriate. Missing baseline data will be imputed using regression imputation. For the primary endpoint, statistical analyses will be performed according to the per-protocol (PP) principle as well as the intention to treat (ITT) principle. Both PP and ITT analyses must demonstrate non-inferiority in order to conclude that immediate CAS during EVT is non-inferior to a deferred treatment strategy.

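### The stated 80% power at 610 patients is about 72% under the protocol's own 95% confidence-interval rule, and the 15% covariate saving is not established for a margin fixed at 0.8

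*Protocol*

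**What the plan says.** Protocol section 4.5 fixes the assumed effect as a "common odds ratio (cOR) of 1.15 for a shift in favorable direction on the full mRS" and says "The non-inferiority margin was set to a cOR of 0.8". Success means that the "lower bound of the cOR 95% confidence interval (CI) does not cross the non-inferiority margin of 0.8". From a simulation with 5000 runs it concludes that "a sample size of 610 patients, would provide 80% power (at a two-sided alpha level of 0.05").

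Three steps follow. Covariate adjustment "results in a reduction of at least 15% in the required sample size (n=520"). A factor of 1.13 for 6% crossover gives 588. A 2% allowance for loss to follow-up and erroneous inclusions gives 600.

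Section 10 adds that "Both PP and ITT analyses must demonstrate non-inferiority in order to conclude" non-inferiority. Section 10.2 makes the primary estimate a covariate-adjusted proportional odds cOR with a 95% confidence interval. Neither section gives a separate margin for the adjusted model.

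**The concern.** Section 4.5 prints everything needed to check the power: effect, margin, error level, decision rule, allocation and mRS distribution. The stated 80% does not come back from them.

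The later reduction to 520 also applies a percentage saving without regard to the margin. In a proportional odds model, adjusting for prognostic covariates does not shrink the standard error of the log cOR. It raises power mainly by moving the conditional effect further from 1. When the test is against a fixed 0.8, only the part of the distance between 1 and 1.15 can grow; the part between 0.8 and 1 cannot.

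What is at stake is the planned chance of a conclusive result. At the assumed effect, the risk of failing to show non-inferiority would be nearer 30% than 20% without the saving.

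**Working it through.** **Inputs (section 4.5).** True cOR 1.15; margin 0.8; 1:1 allocation; lower limit of the two-sided 95% CI, z = 1.960; deferred-arm mRS 0-6 of 6.9, 20.2, 17.9, 16.4, 17.2, 8.0 and 13.4%.

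**1. The plan's chain after 610.** 610 × 0.85 = 518.5 (printed as 520); 520 × 1.13 = 587.6, so 588; 588/0.98 = 600. These steps are arithmetically sound. The problem lies in the starting 610 and in the 15%.

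**2. Standard error.** Whitehead's formula is SE = √[12 / (N(1 − Σp̄³))], where p̄ is the mean of the two arms' category probabilities. Shifting the deferred distribution by cOR 1.15 gives p̄ of about 0.074, 0.212, 0.182, 0.163, 0.167, 0.076 and 0.126. Then Σp̄³ = 0.0273 and 1 − Σp̄³ = 0.9727. At N = 610, SE = √(12/593.3) = 0.142.

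**3. Power at 610.** The distance is ln(1.15/0.8) = 0.1398 + 0.2231 = 0.3629.
- 95% CI: Φ(0.3629/0.1422 − 1.960) = Φ(0.592) = 72.3%. A simulation of 20,000 fitted proportional odds models gives 72.0%; one of 5,000 gives 71.2%.
- One-sided 5% (90% CI): Φ(2.552 − 1.645) = 81.8%.

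Monte Carlo error with 5000 runs is about 0.6 points at 80%, so it does not explain a gap of 8 points. Using the pooled or the immediate-CAS distribution as base gives 72.2-72.3%.

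**4. N for 80% power.** N = 12(1.960 + 0.842)² / (0.9727 × 0.3629²) = about 735. At one-sided 5% it is about 579. Carrying 735 through the plan's own later steps: 735 × 0.85 / 0.94² / 0.98 = about 722.

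**5. Power at 600 enrolled.** Analysed: 600 × 0.98 = 588, SE = 0.1449. Crossover is treated as multiplying the log cOR by 0.94, giving a distance of 0.94 × 0.1398 + 0.2231 = 0.3545. The full 15% saving is treated as an effective N of 588/0.85 = 692.

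| | No crossover | 6% crossover |
|---|---|---|
| No covariate saving | 70.7% | 68.7% |
| Full 15% credited | 77.6% | 75.6% |

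Without a saving, 588 analysed patients reach 80% power at a true cOR of about 1.20, or about 1.21 with crossover.

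**6. The covariate saving against a fixed margin.** As an illustration, suppose a 15% saving for a test against 1 comes entirely from a larger log cOR. That requires a factor 1/√0.85 = 1.085. The distance to the margin becomes 1.085 × 0.1398 + 0.2231 = 0.3747, and the saving is 1 − (0.3629/0.3747)² = about 6%. Simulation with a normal prognostic score (SD 0.7, chosen to give roughly a 15% saving against 1) puts the saving at about 5% if 1.15 is the marginal cOR and about −1% if it is already the adjusted cOR. Adjusted power at N = 600, before crossover, was 73.8% and 69.2% respectively.

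**7. The assumed effect.** The cumulative odds ratios from the two printed distributions, from mRS 0 versus 1-6 up to 0-5 versus 6, are 2.94, 1.81, 1.61, 1.56, 1.39 and 1.20. A proportional odds fit gives a cOR of about 1.70. All six exceed 1.15.

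**The case against.** The strongest reply concerns the covariate saving. Section 4.5 presents 15% as a minimum. With much stronger covariates (savings of 33-47% against 1) and 1.15 read as marginal, simulated adjusted power at 610 rises to 78-82%. If the margin were also translated to the adjusted scale, most of the saving would return. This stands: a reader might infer that the true saving is about 6% or nothing, but the protocol gives neither the covariate strength nor the scale of 1.15 and 0.8, so no single replacement figure is supported. Nor can the type of trial behind the cited saving be judged from the protocol.

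A reader might also infer that the simulation used a 90% CI. That is possible, since it gives about 82% at 610, but it is not shown. The match is inexact (579 patients would suffice for 80%), and a cOR of about 1.19 with the 95% rule would also give 80% at 610.

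Third, the printed distributions imply a much larger effect, with power above 99%, so the trial might be thought amply powered. The protocol does not plan on that effect; it assumes 1.15. The mismatch is a further inconsistency and does not rescue the 80%.

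Finally, the decision rule, margin and type I error are untouched. That is right, and it is why the remedy is a restatement.

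**Conclusion.** The stated power is wrong as written: about 72% at 610 instead of 80%, with about 735 patients needed for 80% before any adjustment. At the planned 600, power at cOR 1.15 is about 69-71% without the covariate saving and about 76-78% with all of it credited, so the shortfall does not depend on how the saving is settled. These figures rest on proportional odds, the printed deferred-arm distribution, a margin of 0.8 on the scale analysed, and crossover diluting the log cOR by 6%. Requiring both ITT and PP to succeed can only lower them.

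The 15% saving is unestablished for a fixed margin, and it may be much smaller. That part is conditional on covariate strength and scale, and carries less certainty than the arithmetic at 610.

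**What to change.** Keep the 95% CI rule and the 600 patients; do not move to a 90% CI to recover the figure. In section 4.5:

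- Rerun the simulation with the adjusted model, the 95% CI, the fixed margin of 0.8 and the joint ITT and PP criterion, and state the confidence level used.
- Say whether 1.15 and 0.8 are on the marginal or the adjusted scale.
- Justify the 15% saving for a fixed margin, or remove it.
- Restate the power: on present figures about 70% at cOR 1.15 without the saving, and 80% at a cOR of about 1.20-1.21, to be replaced by the rerun results.
- Reconcile the assumed 1.15 with the two printed mRS distributions, or explain why the smaller effect was chosen.

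The cost is one simulation and revised wording, with no added patients. The downside is that the stated power becomes less favourable.
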